6. SELECTION AND ENROLLMENT OF PARTICIPANTS

6.1 Inclusion Criteria

- ≥18 years of age,
- Acute myocardial infarction, STEMI and NSTEMI
- Ability to use the device at home
- Must have smartphone device with home wi-fi/mobile internet which allow 24/7 ability to transmit ECG
- Caring family member who will be able to perform the ECG in case the patient himself won't be able to do it

6.2 Exclusion criteria

- <18 years of age
- No ability to use the device at home / Unable to comply with the device instructions
- No smartphone device or home wi-fi/mobile internet which prevent 24/7 ability to transmit ECG
- Unable to download the smartheart application
- No support in home environment
- Out of hospital cardiac arrest
- Resident of nursing home or acute care facility
- Uninterpretable ECG at discharge – left bundle branch block, pacemaker dependence, implantable cardioverter defibrillator.
- Out of hospital cardiac arrest: secondary to a non-shockable rhythm, unrelated to an acute coronary syndrome, or with any level of neurologic damage.
- Patients who are planned for staged PCI after the index hospitalization

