5. STUDY DESIGN

This study will be conducted as a prospective, randomized pilot study in patients with acute myocardial infarction which have undergone coronary angiography with two study groups (Figure 1):

- **Group 1 (control group):** standard clinical practice medical therapy at discharge, including double antiplatelet therapy (DAPT), high potency statins and if indicated, beta blockers.
- **Group 2 (intervention group):** standard clinical practice medical therapy as above plus the Smarheart home-telemonitoring 12 lead ECG device.

Figure 1: Trial outline

Patients will be randomized at discharge to standard medical therapy (DAPT, high potency statins and beta blockers) or the standard medical therapy plus the Smartheart home-telemonitoring 12 lead ECG device. The intervention group will have instructions and explanation, prior discharge, how to use the device and will be guided to have two device testing's at home during the first two weeks after discharge. In case of any symptoms, including but not limited to chest pain, shortness of breath, sensation of irregular heart beats and near fainting during the 90 days post discharge the patient will record a 12 lead ECG at home and transmit it directly to Saint Mary's Hospital CICU designated study NP/PA, which is available 24/7, the ECG will be read by the NP/PA (with the support of the CICU consultant). Communication with the patient will be through the study designated CICU NP/PA, which will call the participant, record short history of the medical emergency and provide the patient with appropriate directions according to the ECG finding, medical urgency and study protocol. The CICU NP/PA will call the patient as soon as possible after receiving the ECG to the study email inbox.

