8. STUDY PROCEDURES

8.1.1 Screening Evaluation

Acute myocardial infarctions patients identified on cardiology service will be evaluated for enrollment. These patients will be approached by a trained research member who will present the background, rationale, and details of the study. A single informed consent form will be used that describes both the screening and study procedures. Those who consent will be asked additional questions of their past medical history and their records will be reviewed to identify any exclusion criteria. If any are present, these will be charted in the screening log. For those who are eligible but refuse, a comment will be added to the screening log detailing the reason for non-participation.

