8.1.2 Enrollment, Baseline, and/or Randomization

All patients who consent to the study are considered to be enrolled as of the date of the consent.

Baseline Assessments- comprises a review for any cardiovascular diseases or risk factors, home medications. Additional data will be collected: type of AMI (location: anterior, inferior, posterior, lateral), troponin levels, baseline ECG, left ventricular function by echocardiography, Canadian Classification scale (CCS) of Angina(class I, II, III IV) .

Randomization- will be done once all inclusion and exclusion criteria are reviewed and the patient meets eligibility criteria. Patient and treating cardiologist will be informed which study group the patient was assigned. Patients assigned to group 1 will be discharged with standard medical therapy as indicated by AHA/ACC guidelines in post AMI patients treated with or without PCI. Patients in group 2 will be discharged with the standard medical treatment as indicated by AHA/ACC guidelines in post AMI patients treated with or without PCI plus they will receive the Smartheart 12 lead ECG home telemonitoring device for the period of 90 days (+/-7). Those patients will have short explanation on how the device works, how to adjust it on the chest and how to transmit the ECG.

A post-study questionnaire will be administered to patients randomized to the device group to collect feedback on their experiences with the device. Participation is voluntary, and responses will be anonymized to ensure confidentiality. The inclusion of this questionnaire will not impact the primary study objectives or patient safety.

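### Device ability is an eligibility criterion for both arms but is first tried out after randomization and in group 2 only, and nothing prevents group 2 patients who fail from being removed and replaced

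*Combined protocol and SAP*

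**What the plan says.** Section 6.1 requires "Ability to use the device at home". Section 6.2 (exclusion criteria) excludes "No ability to use the device at home / Unable to comply with the device instructions" and "Unable to download the smartheart application". These criteria apply to every candidate, whichever arm follows.

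On timing, 8.1.2 states: "Randomization- will be done once all inclusion and exclusion criteria are reviewed and the patient meets eligibility criteria". On method, 8.1.1 states: "Those who consent will be asked additional questions of their past medical history and their records will be reviewed to identify any exclusion criteria". Section 6.2 (study enrollment procedures) adds a screening log in which the reason for exclusion is marked. No section describes handling the device or sending a test ECG before allocation.

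After allocation the arms part:

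- Section 5: "The intervention group will have instructions and explanation, prior discharge, how to use the device". Two device tests follow, "at home during the first two weeks after discharge".
- Section 7: the device is supplied to the intervention group, for a period counted from randomization.
- Section 8.1.2, of group 2: "Those patients will have short explanation on how the device works, how to adjust it on the chest and how to transmit the ECG".
- Schedule of Evaluations (8.1): the follow-up ECG and training calls at weeks 1, 2 and 4 are coded for the study group only.

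Section 10.3.4 (protocol deviations) begins with the device-testing calls. It then provides that deviations are flagged, that the study team decides whether one precludes further participation, and that a patient so judged is removed and replaced. Section 9.6 specifies a chi-square test of the combined endpoint and does not say which patients are analysed.

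**The concern.** A criterion that can only be fully tested by using the device is tested in one arm. Suppose a group 2 patient proves unable to place the device or transmit. That patient now appears to meet a listed exclusion, and the study team, who know the allocation, learn of it on a call that group 1 never receives. Read together, 10.3.4 and 9.6 leave the team free to remove and replace the patient. The group 1 counterpart is never put to the test and stays.

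If patients who cannot manage the device also have more ED visits, readmissions or testing, one-sided removal lowers the group 2 event rate without any device effect. The error favours the device, on the primary endpoint.

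**Working it through.** **Inputs from the plan.** Section 9.2: event rate 48%, 120 per arm, 37.5% reduction, alpha 0.05, beta below 0.2. Section 9.6: chi-square test. Sidedness is not stated; I take it as two-sided.

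**The plan's own figure.** 0.48 × (1 − 0.375) = 0.30. With 120 per arm and pooled variance, power for 48% against 30% is 82.0%, which agrees with beta below 0.2. That figure is not in dispute.

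**Assumptions not in the documents.** A share x of patients cannot use the device (5, 10 or 15%). Their event rate is R times that of users. All of them in group 2 are removed and replaced, so 120 are still analysed. There is no true device effect.

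**Formulas.** Group 1 keeps the mixture at 0.48. Group 2 contains only users, whose rate is

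u = 0.48 / (1 − x + xR).

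With d = 0.48 − u, p̄ = (0.48 + u)/2, SE0 = √(2p̄(1 − p̄)/120) and SE1 = √((0.48 × 0.52 + u(1 − u))/120), the probability of rejection is

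Φ((d − 1.96·SE0)/SE1) + Φ((−d − 1.96·SE0)/SE1).

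**Worked case, x = 10%, R = 1.5.** u = 0.48/1.05 = 0.4571 and d = 0.0229. SE0 and SE1 are both 0.0644. Rejection = Φ(−1.605) + Φ(−2.315) = 0.054 + 0.010 = 0.064.

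| R | x | Group 2 rate u | Implied non-user rate (R·u) | Difference (points) | Type I error |
|---|---|---|---|---|---|
| 1 | any | 48.0% | 48% | 0 | 5.0% |
| 1.5 | 5% | 46.8% | 70% | 1.2 | 5.4% |
| 1.5 | 10% | 45.7% | 69% | 2.3 | 6.4% |
| 1.5 | 15% | 44.7% | 67% | 3.3 | 8.1% |
| 2 | 5% | 45.7% | 91% | 2.3 | about 6% |
| 2 | 10% | 43.6% | 87% | 4.4 | about 10% |
| 2 | 15% | 41.7% | 83% | 6.3 | about 16% |

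For R = 1.5 and x = 15%, u = 0.48/1.075 = 0.44651, so d = 0.03349, or 3.3 points. The two-fold rows imply event rates of 83 to 91% in non-users and should be read as an upper bound.

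**If everyone is kept and analysed as assigned.** There is no selection, only dilution. Let the true effect be 48% to 30% and let non-users stay at 48%. The group 2 rate is then (1 − x) × 0.30 + x × 0.48, that is 30.9, 31.8 or 32.7%. Power falls from 82.0% to 77.7, 72.9 or 67.8%.

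**The case against.** The strongest reply is that the documents never say that inability to use the device leads to removal. Section 10.3.4 concerns deviations in general, is discretionary and does not name device inability. Where the plan does deal with device difficulty, it points to keeping the patient. Section 5 covers unresolved technical problems by a phone recommendation, section 7 sends reminders for missed test ECGs, and the Schedule allows a further week 4 contact for those who need more training. This stands. A reader might infer that the plan prescribes a one-arm exclusion, or that the type I error is inflated as things are. The text supports only that the route is open.

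A reader might also infer that screening cannot detect any of the device-related failures. That goes too far. App download needs only the patient's own phone, and 8.1.1 does not say that interview and records are the only means used. Smartphone, internet and home support can be asked about in both arms. Section 6.1 also requires a family member who can perform the ECG, so a patient's own inability is not automatically an exclusion. These points shrink the affected group. What remains is practical inability that shows only when the device is used.

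Finally, instruction after allocation is ordinary when one arm has no device, and does no harm to validity if all randomized patients are analysed as assigned. I agree, but the plan does not say that they will be.

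**Conclusion.** The point holds as an open route to one-arm exclusion, not as a demonstrated bias. It takes three things together: a both-arm criterion first tried out in group 2, a discretionary remove-and-replace rule next to the device-testing calls, and no stated as-randomized analysis set.

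Under the 1.5-fold assumption the effect is modest: 1.2 to 3.3 points and a type I error of about 5.4 to 8.1% for 5 to 15% removed. It reaches about 16% only at the two-fold upper bound, and is nil if non-users carry the same risk as others. The share unable, their relative risk and complete removal are all assumptions. The Schedule's Day 0 row for providing the device and instructions does not itself show order or arm; sections 5, 7 and 8.1.2 do. The change is worth making because it closes the route at almost no cost.

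**What to change.** 1. In 6.2 (exclusion criteria) and 8.1.2, state that the device and app criteria are judged only before randomization and in the same way for every candidate. Include a download of the app on the patient's own phone at screening, with the result in the screening log.
2. In the same places, state that device difficulty found after randomization is non-adherence, not an eligibility failure.
3. In 10.3.4, state that such patients are neither removed nor replaced.
4. In 9.6, state that all randomized patients are analysed in the group to which they were assigned.

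The cost is protocol wording and a few minutes per candidate for the app check. Retained non-users dilute the effect, with the loss of power shown above under those assumptions.

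A supervised test transmission by every candidate before allocation would reduce that dilution. It is optional: it needs devices on hand for screening and briefly exposes controls to the device.

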Number of Subjects	240 patients in total, enrolled over one-two years

Inclusion and Exclusion Criteria	
Inclusion criteria:
 
 • ≥18 years of age, • Acute myocardial infarction, both STEMI and non-STEMI • Able to use the home ECG telemonitoring • Must have smartphone device with home wi-fi/mobile internet which allows 24/7 ability to transmit ECG • Caring family member who will be able to help/perform the ECG in case the patient himself won't be able to do it • Planned to be discharged home by the treating team 
Exclusion criteria:
 
 • No ability to use the device at home • No smartphone device or home wi-fi/mobile internet which prevent 24/7 ability to transmit ECG • Cannot download the smartheart app • No support in home environment • Out of hospital cardiac arrest: secondary to a non-shockable rhythm, unrelated to an acute coronary syndrome, or with any level of neurologic damage. • Resident of nursing home or acute care facility • Uninterpretable ECG at discharge – left bundle branch block (LBBB), pacemaker or implantable cardioverter defibrillator (ICD) with pacing dependence. • Patients who are planned for staged PCI after the index hospitalization
Study Product, Dose, Route, Regimen	Prior to discharge patients will be 1:1 randomized to standard medical therapy or standard medical therapy + 12 lead ECG Smartheart telemonitoring device.
Duration of Administration	Patients will receive the device for the period of 90 (+/-7) days .
Reference therapy	Group 1 will serve as the reference group
Statistical Methodology	Inter-group differences in the rates of the primary combined endpoint will be analyzed by the Chi square test.

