6.2 Study Enrollment Procedures

This study will be conducted on a study platform that is already in place at the Mayo Clinic Rochester. Patients identified with a diagnosis of acute myocardial infarction and subsequent coronary angiography will be enrolled. Any potential study candidates will be identified based on the eligibility criteria listed above. A screening log will be kept and secured electronically. Those potentially eligible will be recorded by clinic number and exclusion criteria will be checked. If any are met, the specific reason will be marked, otherwise a commentary will be entered for those who are eligible but do not wish to participate. Those patients who agree to participate will be asked to provide written consent. The study details will be outlined. It will be made clear that at this point there are no data whether the intervention approach leads to superior clinical outcomes and this very fact provides the rationale for this trial.

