10.3.4 Protocol Deviations

Patients will be contacted by phone for the device testing several times during the first month. The next contact will occur by phone call at the end of the study (90 +/- 7 days after the randomization). If any deviation from the study protocol were noted, a record will be made on their study participation form and these patients will be flagged for review by the PI. The study team will then decide if a study deviation occurred that precludes continuation of study participation. If this were indeed the case, the patient will be notified. This individual will be removed from the study and will be replaced by another study participant.

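### The study summary and Section 6.2 set different exclusion rules for out-of-hospital cardiac arrest, and nothing says which list governs

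*Combined protocol and SAP*

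**What the plan says.** Eligibility is set out twice, in the Section 1 summary table and in Sections 6.1 and 6.2.

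**Cardiac arrest.** Section 6.2 (Exclusion criteria) has a bullet that reads in full "Out of hospital cardiac arrest". Three bullets further down, the same list has "Out of hospital cardiac arrest: secondary to a non-shockable rhythm, unrelated to an acute coronary syndrome, or with any level of neurologic damage". The summary carries the second form and has no unqualified bullet.

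**ICD.** Section 6.2 has "Uninterpretable ECG at discharge – left bundle branch block, pacemaker dependence, implantable cardioverter defibrillator". The summary has the same lead-in about the discharge ECG, but its device wording is "pacemaker or implantable cardioverter defibrillator (ICD) with pacing dependence".

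**How the criteria are used.** Under Study Enrollment Procedures, which is also numbered 6.2, exclusion criteria are checked at screening: "If any are met, the specific reason will be marked". Section 8.1.2 places randomization after the criteria have been reviewed and met, and has the patient and treating cardiologist told the arm.

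**What can follow.** Section 10.3.4 sends any protocol deviation to the principal investigator for review. If the study team decides that the deviation rules out continuing, then "This individual will be removed from the study and will be replaced by another study participant".

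**The concern.** Both lists are current text, and screeners can work from either. If the lists disagree about a recognisable type of patient, enrolment depends on which page was open, and the summary and the body describe different trial populations.

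There is a second, more indirect concern. If a patient is enrolled on the summary wording and later checked against Section 6.2, someone could call the enrolment a deviation. Section 10.3.4 would then offer a route to remove and replace a randomized patient. Allocation is open, Section 9.6 names no analysis population, and Section 13 provides no adjudication committee. A removal decided after the arm is known would weaken the comparison that randomization is meant to protect.

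**Working it through.** No figure in the plan bears on this point and none needs reproducing. The check applies each list to the patients on whom the lists might differ.

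Inputs: the exclusion list in the Section 1 summary, the exclusion list in Section 6.2, and the enrolment rule that meeting any one criterion is enough to exclude.

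| Patient (no other exclusion applies) | Summary | 6.2, qualified arrest bullet | 6.2, unqualified arrest bullet | 6.2 as a whole |
|---|---|---|---|---|
| A. Arrest with a non-shockable rhythm, or not due to ACS, or with neurologic damage | Excluded | Excluded | Excluded | Excluded |
| B. Arrest with a shockable rhythm, due to ACS, no neurologic damage | Not excluded | Not excluded | Excluded | Excluded |

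Patient A is treated the same everywhere. Patient B is not: the summary lets this patient in and Section 6.2, applied on an any-criterion basis, keeps the patient out.

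Within Section 6.2, everyone caught by the qualified bullet is already caught by the unqualified one. The qualified bullet therefore excludes nobody further and is redundant. Its detail still suggests that some arrest survivors were meant to be eligible, which is what the summary allows.

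| Patient (no other exclusion applies) | Summary | 6.2, read as a plain list | 6.2, read under its lead-in |
|---|---|---|---|
| C. ICD, pacing dependent | Excluded | Excluded | Excluded |
| D. ICD, not pacing dependent, interpretable ECG at discharge | Not excluded | Excluded | Not excluded |

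For patient D the answer depends on whether the devices in "left bundle branch block, pacemaker dependence, implantable cardioverter defibrillator" are exclusions in their own right or examples of an uninterpretable ECG. On the second reading the two lists agree.

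The last step was to look for a precedence rule. No section says that the summary or the body governs. The enrolment text points to the criteria listed above it, which directly follows Sections 6.1 and 6.2, but it does not say that the summary yields to them.

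**The case against.** **The bullets in Section 6.2 do not contradict each other.** This stands. A reader might infer that Section 6.2 is internally contradictory, but when any single criterion excludes, the broad bullet absorbs the narrow one. The list is redundant, and the real conflict is with the summary.

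**Section 6.2 is the working list.** Its position just before the enrolment procedures supports this. It is not stated, however, and if it is true the summary misdescribes who may enter.

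**The ICD wording can be reconciled.** This largely stands. A reader might infer that Section 6.2 bars every ICD patient. The shared lead-in about the discharge ECG permits a narrower reading that matches the summary, so an eligibility reversal is not demonstrated.

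**The link to removal is an inference.** This stands in part. Section 8.1.2 settles eligibility before randomization, and Section 10.3.4 does not name an ineligible enrolment as a deviation. Its scope is nevertheless any deviation from the protocol, so the route is not closed. Removal and replacement after randomization is also an issue in its own right, whatever the arrest wording, and this point should not borrow its weight.

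**No effect on the results can be shown.** This stands. A reader might infer a shift in MACE or in the primary endpoint, or that these patients are at especially high arrhythmic risk. The documents give neither a count of such patients nor a risk figure for them. The background section ties markedly increased risk to reduced ejection fraction, not to these two groups.

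**Conclusion.** The inconsistency on cardiac arrest is real and should be corrected. One clearly defined type of patient, the neurologically intact survivor of a shockable, ACS-related arrest, is eligible under the summary and excluded under Section 6.2, with no stated precedence. The ICD difference is a secondary ambiguity that a consistent reading can resolve.

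The size is unknown. The documents do not say how many of the planned 240 patients fall in either group, and no effect on event rates or power should be attached to this point. It would also go too far to call the trial population undefined: the uncertainty is confined to two narrow groups at a single site.

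The conclusion on cardiac arrest rests only on the current wording of the two lists and on the any-criterion rule. The link to Section 10.3.4 rests on the further assumption that an enrolment judged ineligible would be handled as a deviation. That assumption supports a safeguard but does not support a claim of bias.

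**What to change.** 1. Reconcile the Section 1 summary and Section 6.2 so that each has a single cardiac-arrest criterion in identical words. Which criterion to keep is for the investigators to decide.
2. Do the same for the ICD item. State whether the device alone excludes or only a device that makes the discharge ECG uninterpretable, and make clear which devices the pacing condition covers.
3. Add a sentence that any patient already randomized under either wording is analysed in the assigned arm and is not removed or replaced under Section 10.3.4 on that ground.

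The cost is a wording amendment. It needs no change to the sample size, the visits or the data collected.
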